Appendix 7 – EORTC QLQ-C30 specimen questionnaire

Please click on the link below or copy and paste it into your browser. **A Norwegian version** is available in Investigator Site File.

http://groups.eortc.be/qol/sites/default/files/img/slider/specimen_qlq-c30_english.pdf

Appendix 8 – EORTC QLQ-CIPN20 questionnaire

The form can be requested from [contact]. **A Norwegian version** is available in Investigator Site File.

Chemotherapy-induced peripheral neuropathy (CIPN) is a major, potentially dose-limiting side effect of various chemotherapeutic agents. The CIPN20 is a 20-item quality of life questionnaire, which has been developed to elicit patients' experience of symptoms and functional limitations related to CIPN. The CIPN20 has 3 subscales: a sensory, a motor, and an autonomic subscale. In combination with the more classical, physician-based clinical rating scales, the CIPN20 should yield a more complete picture of the nature, frequency, and severity of CIPN in a wide range of oncology patient populations.

Appendix 9 – EQ-5D-5L questionnaire user guide

Please click on the link below or copy and paste it into your browser. **A Norwegian version of the questionnaire** is available in Investigator Site File.

https://euroqol.org/wp-content/uploads/2016/09/EQ-5D-5L_UserGuide_2015.pdf

Appendix 10 – Council for International Organizations of Medical Sciences (CIOMS) Suspect Adverse Reaction Report form

Please click on the link below or copy and paste it into your browser:

http://www.basg.gv.at/fileadmin/_migrated/content_uploads/CIOMS_form.pdf

## **1. Introduction**

### **1.1. Background and rationale**

Owing to an aging population, colorectal cancer (CRC) is a common malignancy with a sharp rise in incidence from the age of 60. Immune checkpoint blockade (ICB) is efficacious in the small CRC subgroup of patients with highly immunogenic disease, the microsatellite-unstable/mismatch repair (MMR)-deficient entity. ICB is, however, considered inefficacious for the majority of patients presenting microsatellite-stable (MSS)/MMR-proficient CRC. Unresectable abdominal metastases commonly reflect an aggressive phenotype.

Our previous findings for short-course oxaliplatin-containing chemotherapy in locally advanced or early metastatic CRC support a notion that oxaliplatin may invoke tumor-defeating immunity. Specifically, patients who presented unresectable single-organ liver metastases as the first metastatic event, given oxaliplatin as hepatic arterial infusion chemotherapy and responding with a rapid rise in a circulating anti-tumor immune factor, were alive 8-12 years later.

In the METIMMOX trial, patients with previously untreated, unresectable abdominal metastases from MSS-CRC will be randomly assigned to short-course oxaliplatin-based chemotherapy (the Nordic FLOX regimen) alternating with ICB (nivolumab) or standard FLOX chemotherapy.

### **1.2. Objectives**

*Primary objective:* To determine progression-free survival (PFS), in terms of failure of treatment strategy, on sequential treatment with the Nordic FLOX regimen and nivolumab compared with the standard-of-care Nordic FLOX regimen in previously untreated metastatic MSS-CRC.

*Secondary objectives:*

- i) To determine safety and tolerability of sequential treatment with the Nordic FLOX regimen and nivolumab compared with the standard-of-care Nordic FLOX regimen.
- ii) To determine objective response rate (ORR), duration of response (DOR), secondary surgical curative resection rate (SSCRR), and overall survival (OS).
- iii) To monitor and compare quality-of-life (QoL) alterations during therapy courses.

*Tertiary objective:* To compare costs for the resource use (in diagnostic work-up, treatment, and any adverse events) for the sequential therapy with that of the standard-of-care, applying a model specifically developed for CRC.

*Exploratory objectives:*

- i) To develop circulating biomarkers of cytotoxic T lymphocyte activity.
- ii) To develop circulating biomarkers of tumor response.
- iii) To develop circulating biomarkers of immunogenic cell death.
- iv) To develop functional MR imaging biomarkers.
- v) To develop histologic and molecular tumor biomarkers.

## **2. Study Methods**

### **2.1. Trial design**

The METIMMOX study is a multicenter open-label randomized phase 2 trial in first-line treatment of metastatic MSS-CRC using the standard-of-care Nordic FLOX regimen (control arm) or sequential therapy with the Nordic FLOX regimen and nivolumab (experimental arm), to investigate whether the experimental arm shows superiority in PFS, safety, tolerability, and QoL.

## Study period

- Estimated date of first patient enrolled: 1 March 2018
- Anticipated recruitment period: 12 months
- Estimated date of last patient completed: 1 September 2020

## Treatment duration

- Expected treatment duration per patient:
  - Experimental arm: 18 months (until failure of treatment strategy)
  - Control arm: 9 months (until failure of treatment strategy)

## Follow-up:

- Expected follow-up period per patient:
  - Experimental arm: 30 months (12 months following failure of treatment strategy)
  - Control arm: 21 months (12 months following failure of treatment strategy)

## 2.2. Randomization

The patients will be block-randomized into treatment arms with ratio 1:1 following a computer-randomized allocation sequence. The blocks will be defined according to sidedness and (K)RAS/BRAF mutation status of the primary tumor (right-sided versus left-sided and (K)RAS/BRAF wild-type versus mutation). The allocation sequence will be generated by the web-based Viedoc system.

## 2.3. Sample size

Calculation of sample size was performed for PFS – the primary end point – and based on PFS data from recent publications. A median PFS of 9 months was assumed for the standard-of-care (control arm) [Cartwright, 2012; Tveit et al., 2012; Cremolini et al., 2015]. Regarding the therapy concept of ICB, there is no PFS data published as yet for the setting of interest. In the study of patients with treatment-refractory metastatic CRC, median PFS was not reached in the cohort with mismatch repair-deficient disease at the time of reporting [Le et al., 2015]. In the study of previously untreated patients with advanced non-small cell lung cancer, which is a tumor entity with considerably poorer prognosis than advanced CRC, patients with PD-L1-positive tumors that were randomized to ICB showed median PFS of 10.3 months compared to 6.0 months for standard chemotherapy [Reck et al., 2016].

Extrapolating to the setting of interest, with a median PFS of 9 months for standard-of-care, a median PFS twice as long (18 months) was entered for the sequential therapy. Assuming the exponential distribution of survival functions, the median PFS estimates were converted to hazard ratio (HR) of 0.5. Allowing for 10% censoring rate of subjects, the required sample size was estimated to be 40 patients in each arm to be able to show that HR of 0.5, implying the risk of a PFS event in the experimental group is 50% lower than in the control group, is significantly different from 1 with the power of 80% at significance level of 5%, given that log-rank test will be used.

However, it was necessary with several adjustments of the above calculations to maintain sufficient power. First, the sample size was adjusted to enable removal of a maximum of 5% enrolled cases with non-MSS tumor before data analysis. Next, keeping in mind the condition of patients, it is not unlikely that some will be lost from the study before a valid PFS event has been reached. Also, a number of analyses stratified by primary tumor sidedness and (K)RAS/BRAF mutation status will be performed. Hence, to enable high enough power in the statistical analysis, the sample size was increased by an additional 20%. After

incorporating the adjustments, the final sample size was estimated to be 100 patients, 50 in each arm, with 1:1 randomization.

With the total catchment populations of the participating centers we envisage an accrual duration period of approximately 12 months to procure the sufficient number of study cases. As there is no PFS data published as of yet for the novel therapy concept of repeat sequential immunogenic chemotherapy and ICB, and further, the optimum duration of immune-modulating therapy is currently unknown, the study duration of the expected METIMMOX longer-lasting arm (experimental arm) was estimated to 30 months (12 months following failure of treatment strategy). Because these estimates were pure conjecture, they were not entered into the sample size calculation.

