7.8 End of study

The end of study is defined as “last patient last visit”, in accordance with European Commission guidelines. However, as mentioned in [Paragraph 5.5](#), accumulating evidence from a number of clinical trials in different tumor types with nivolumab indicates that patients may obtain durable responses, even if they discontinue nivolumab for toxicity. Such observations are acknowledged as general features of ICB [Emens *et al.*, 2017] and may call for a redefinition of the end-of-study term during the study conduct.

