#### 5.2. Analysis methods

*Main statistical analyses.* The main statistical analysis is planned after the last patient has fulfilled the pre-defined follow-up period. PFS will be calculated from the day of randomization to first recorded disease progression according to RECIST v1.1 or when applicable iRECIST, or death. Patients who have not had disease progression at the time of final analysis will be censored at the date last known to be alive and progression-free. The analyses will compare the treatment groups in total as well as groups stratified by primary tumor sidedness and (K)RAS/BRAF mutation status.

*Interim analyses.* Interim analyses will apply to data on safety, tolerability, possible detrimental effects, and curative outcomes, and will be based on purely clinical judgment by the External Data and Safety Monitoring Committee. These types of data will be reported as the number of events.

*Descriptive statistics.* Demographic and clinical characteristics will be presented as means and standard deviations, medians with minimum and maximum values, or frequencies and percentages, as appropriate. Further statistical analyses will be separated to primary analyses, including only comparison of primary end point between two treatment arms, and secondary analyses, including stratified analyses on primary and secondary end points as well as number of analyses on secondary end points.

*Primary analysis.* Median PFS time will be compared between study arms by drawing Kaplan-Meier survival curves and performing log-rank test. HR with the corresponding 95% CI and p-values will be estimated by Cox proportional hazards model.

*Secondary analyses.* Distribution of PFS times stratified by the primary tumor sidedness and (K)RAS/BRAF mutation status will be illustrated graphically by Kaplan-Meier curves and compared by log-rank test. To assess the hazard rates for disease progression within each strata, Cox proportional hazards model will be estimated and, if appropriate, adjusted for relevant covariates. The results will be presented as HR with the corresponding 95% CI and p-values.

Safety. The number of serious adverse events (SAE) will be summarized and presented by trial arm. In addition, information will be given on the number of SAE per participant, together with details on the causality, expectedness, and outcome of each SAE experienced. Summaries of suspected unexpected serious adverse reaction (SUSAR) events will also be presented by trial arm.

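### The 10% censoring behind the sample size does not follow from the plan's own medians and timeline, the end date leaves out accrual, and the PFS cut-off has no event count

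*SAP*

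**What the plan says.** SAP 2.3, repeated in protocol 10.1, takes exponential PFS with medians of 9 and 18 months, hence a hazard ratio of 0.5. It gives the base size as "Allowing for 10% censoring rate of subjects, the required sample size was estimated to be 40 patients in each arm", to show that the ratio "is significantly different from 1 with the power of 80% at significance level of 5%, given that log-rank test will be used". Allowances of 5% for non-MSS tumours and a further 20% bring the total to 100. The 20% is justified by patients lost before a PFS event and by the stratified analyses. On accrual and study duration, the same section says: "Because these estimates were pure conjecture, they were not entered into the sample size calculation".

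The calendar in SAP 2.1 and protocol chapter 3 starts with a first patient on 1 March 2018, then "Anticipated recruitment period: 12 months" and "Estimated date of last patient completed: 1 September 2020". Follow-up per patient is given as "Experimental arm: 30 months (12 months following failure of treatment strategy" and as 21 months in the control arm, described in the same way.

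On timing, SAP 5.2 says: "The main statistical analysis is planned after the last patient has fulfilled the pre-defined follow-up period". Patients still progression-free at that analysis are censored. SAP 2.6 adds only that end points mature at different times. Neither document gives a number of PFS events. Protocol 7.8 defines the end of study as the last patient's last visit and notes that durable responses "may call for a redefinition of the end-of-study term during the study conduct".

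**The concern.** Power for a log-rank test depends on events, and the plan converts events to patients through an assumed 10% censoring. With a median of 18 months in one arm, 10% overall requires long follow-up. The calendar does not appear to provide it, and the plan says its durations were not used in the calculation.

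The dates also conflict. The end date is 30 months after the first enrolment, so a patient enrolled at month 12 has 18 months by then, not 30.

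The analysis trigger can be read in two ways: a fixed number of months, or 12 months after each patient's own failure. On the second reading, a patient who has not failed never completes follow-up. Without an event count, nothing tells the sponsor whether the data are mature enough to deliver the stated power.

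**Working it through.** **Inputs.** Medians 9 and 18 months, hazard ratio 0.5, 5% level, 80% power, 10% censoring, 40 per arm (SAP 2.3). First patient 1 March 2018, 12 months' recruitment, end 1 September 2020, follow-up 30 and 21 months (SAP 2.1). Two assumptions are mine: the test is two-sided, and accrual is uniform.

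**1. The plan's own figure.** (1.960 + 0.842)² = 7.849.
- Freedman: 7.849 × [(1 + 0.5)/(1 − 0.5)]² = 7.849 × 9 = 70.6, so 71 events. 71/0.9 = 79 patients, or 40 per arm. This reproduces the plan.
- Schoenfeld: 4 × 7.849/(ln 0.5)² = 65.3, so 66 events. 66/0.9 gives 74 patients, or 37 per arm. This does not match.
- Inflation: 80 × 1.05 × 1.20 = 100.8, consistent with 100.

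The arithmetic is right for its inputs. The question is the 10%.

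**2. Dates.** 1 March 2018 + 30 months = 1 September 2020. A patient enrolled on 1 March 2019 reaches 30 months on 1 September 2021.

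**3. Censoring implied by the medians.** With accrual over A = 12 months, minimum follow-up F and λ = ln 2/median:

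proportion censored = [exp(−λF) − exp(−λ(F + A))]/(λA)

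For a fixed follow-up t per patient it is exp(−λt).

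| Reading | Control | Experimental | Overall |
|---|---|---|---|
| Cut-off 1 September 2020 (F = 18) | 16.3% | 40.0% | 28.2% |
| 21/30 months per patient | 19.8% | 31.5% | 25.7% |
| Cut-off 1 September 2021 (F = 30) | 6.5% | 25.2% | 15.8% |

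The first row depends on accrual shape. It is 20.7% if everyone enrols on day 1 and 37.5% if everyone enrols at month 12. Reaching 10% overall takes about 52 months from first enrolment, and the experimental arm would still be 17% censored.

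**4. Power.** Events = N × (1 − overall censoring). Power is Φ(√events/3 − 1.96) by Freedman and Φ(√events × ln 2/2 − 1.96) by Schoenfeld; ranges run from the first to the second. N = 95 is 100 less the 5% non-MSS exclusion. Lost patients are counted as contributing no event.

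| Analysed patients | 1 September 2020 | 1 September 2021 |
|---|---|---|
| 95 | 68 events, 79–82% | 80 events, 85–87% |
| 95 less 10% (85.5) | 61 events, 74–78% | 72 events, 81–84% |
| 95 less 20% (76) | 55 events, 69–73% | 64 events, 76–79% |

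**5. When 71 events arrive.** From 95 patients, about month 32, with 1 − 71/95 = 25% censored. With 10% lost, about month 40.5. With 20% lost, not before month 42 (1 September 2021).

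**The case against.** The strongest reply is that the documents never name 1 September 2020 as the PFS cut-off. It is an estimate of when the last patient completes, while SAP 5.2 ties the analysis to follow-up. This stands. A reader might infer that 28%, or 40% in the experimental arm, is the plan's own censoring rate. It is one reading, it needs an accrual pattern the documents do not give, and it rests on a date that is itself inconsistent. If follow-up means 12 months after each patient's own failure, there is no administrative censoring and 10% could stand. That reading cannot be guaranteed to fit the stated end date, and the plan does not choose it.

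A second reply is that the inflation to 100 covers the shortfall. It largely does. A reader might infer that the trial is underpowered, or that any loss at all takes power below 80%. The figures do not support that: at the 2020 date 95 patients have 79–82%, and at the 2021 date a 10% loss still leaves 81–84%. What remains is that, at the 2020 date, most of the 20% reserve goes to administrative censoring and not to its stated purposes.

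The 10% might instead be meant as loss to follow-up only. SAP 2.3 lists loss before a PFS event among the reasons for the extra 20%, so that reading leaves administrative censoring with no allowance.

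A reader might also take protocol 7.8 to make the PFS analysis time depend on observed responses. It concerns the end of study and does not mention the PFS cut-off. Amendments need authority and ethics approval (protocol 11.4), and the Study Statistician is kept blind to arm (protocol 10.2.2). The clause is a reason to fix the cut-off separately, not evidence that it will move.

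Finally, the plan openly says durations were left out, and a follow-up-timed phase 2 analysis is not in itself an error. Both points are fair, but neither makes 10% agree with the medians and dates printed beside it.

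**Conclusion.** Wrong as written, with a moderate effect. The 10% is too low on every fixed follow-up reading: about 16% at the most favourable of the three, about 26–28% at the other two. The end date conflicts with 12 months of recruitment plus 30 months of follow-up, and the trigger for the main analysis is ambiguous and carries no event count.

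The consequence depends on which date governs. If it is 1 September 2020, power is about 80% only with almost no losses. If it is 1 September 2021, power holds with 10% lost and falls slightly short (76–79%) with 20% lost. These figures rest on exponential PFS at the planned medians, uniform accrual and 5% non-MSS exclusions. The finding that every fixed-time reading exceeds 10% does not depend on accrual shape at the 2020 date, where the extremes are 21% and 38%.

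**What to change.** In SAP 2.3, 2.6 and 5.2, with matching text in the protocol:

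- State the required number of PFS events as 71, the number behind 40 per arm. Run the primary PFS analysis at that count or on 1 September 2021, whichever comes first.
- Correct the last-patient date to 1 September 2021 so that it includes accrual.
- Replace the 10% with the censoring that belongs to the chosen cut-off: about 25% at 71 events from 95 patients, or about 16% at 1 September 2021. Do not enter 28%, which belongs to the superseded date.
- State that any redefinition of the end of study under protocol 7.8 does not move the primary PFS cut-off. The clause itself can stay.

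The cost is wording and time, with no additional patients. Against the stated end date, the analysis comes about 2 months later with no losses (month 32), about 10 months later with 10% lost (month 40.5), and 12 months later, at the backstop (month 42), with 20% lost. In that last case the analysis would go ahead on about 64 events.

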## **2.4. Framework**

The analyses comparing experimental and control groups will be performed within the framework of superiority hypotheses testing.

## **2.5. Statistical interim analysis and stopping guidance**

Interim analyses will particularly apply to data on safety, tolerability, possible detrimental effects, and curative outcomes, and will be based on purely clinical judgment by the External Data and Safety Monitoring Committee. In particular, CTCAE grade 3–5, PFS measures considerably shorter than 9 months, complete response (CR), and secondary surgical curative resection events will be counted.

## **2.6. Timing of final analysis**

Analyses of the various end point data will not be undertaken simultaneously, as the various end points will not mature simultaneously. For example, some biomarker analyses may be done before the final outcome data are mature.

## **2.7. Timing of outcome assessments**

See 5.1 for end point definitions and time points at which end points will be measured.

# **3. Statistical Principals**

## **3.1. Confidence intervals and P values**

Level of statistical significance is set to 5% in all analyses. Whenever relevant, 95% confidence intervals (CIs) will be reported. No adjustment for multiple testing will be introduced. However, all performed statistical analyses will be reported in the publications leading to transparency and enabling reader to judge the validity of the reported p-values.

## **3.2. Adherence and Protocol Deviations**

Investigators ascertain they will apply due diligence to avoid protocol deviations. All significant protocol deviations will be recorded and reported in the clinical study report.

### **3.3. Analysis populations**

The following study populations will be defined:

- **Intention-to-treat population:** Includes all randomized participants, regardless of protocol adherence. We expect about 5% of randomized patients to have non-MSS tumor. These patients will be excluded from the analysis post-randomization. According to Fergusson and co-workers [Fergusson et al., 2002], such exclusion does not introduce bias and may be legitimate if an independent, blinded adjudication committee makes the decision on exclusion after evaluating all randomized patients. Sample size calculations include necessary adjustments to preserve the same power after exclusion of misdiagnosed patients. The sample size calculation has included necessary adjustments to maintain the same power after exclusion of patients with non-MSS tumor.
- **Safety population:** Includes all randomized participants who have received at least one dose of study medication and had at least one sequential safety-related observation. Subjects who withdraw from the study will be included in the safety analysis given the safety population criteria are otherwise met. A list of withdrawn subjects, preferably with the reasons for withdrawal, will be made.
- **Per-protocol population:** Includes all subjects who have adhered to all protocol-defined treatments and outcome assessments.

We will account for all of the patients registered in the study. The number of patients who are not evaluable, or who die or withdraw before treatment has begun, will be specified. The distribution of follow-up time will be described and the number of patients lost to follow-up will be given. Start of follow-up will be defined as the date of randomization.

